10.3 ANALYSIS DATASETS

Four analysis datasets are possible; however, analyses may not necessarily be conducted with all four:

- **Intention-to-Treat (ITT) Dataset:** all randomized participants.
- **Safety Dataset:** all subjects who received at least one dose of the study agent.
- **Evaluable Dataset:** all subjects who receive all 4 doses.
 - **Per Protocol Dataset:** a subset of the ITT Dataset. A detailed description of the reasons for exclusion from the PP population will be included in the SAP.

The presentation of baseline characteristics will be conducted on the ITT dataset. All safety analyses will be performed for the Safety Dataset. Analyses of the secondary endpoints will focus on the Evaluable and/or Per Protocol Datasets.

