5.4.2 HANDLING OF PARTICIPANT WITHDRAWALS OR TERMINATION

Subjects will be encouraged to complete the study and all assessments. Subjects may voluntarily withdraw at any time, and the investigator may discontinue individual subjects from the study at any time.

Approximately 45 subjects (1:1 ratio of GRF6021 to placebo) will be enrolled in the study with the aim of having 40 evaluable subjects. Evaluable subjects are those who received all 4 doses and had all blood draws for assessment of the primary endpoint. Subjects who discontinue or are unblinded may be replaced. Subjects who withdraw or are withdrawn during screening will be replaced.

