6.1.8 DURATION OF THERAPY

From screening to exit, the duration of study involvement for each subject is approximately 7 to 12 weeks. All subjects will receive 4 infusions over 3 days. The duration of therapy for a subject to be considered evaluable in the intent-to-treat population is 4 doses.

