10 STATISTICAL CONSIDERATIONS

10.1 STATISTICAL DESIGN MODEL AND ANALYTICAL PLANS

Approximately 45 subjects (1:1 ratio of GRF6021 to placebo) will be enrolled in the study with the aim of having 40 evaluable subjects. Evaluable subjects are those who received all 4 doses and had all blood draws for assessment of the primary endpoint.

A Statistical Analysis Plan (SAP) with analytical details and assumptions will be developed and finalized before database lock and unblinding of the study data.

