10.2 STATISTICAL HYPOTHESES

While we hypothesize that active treatment with GRF6021 will modulate the immune response to surgery, because this is an exploratory study, it is not designed to detect statistically significant differences between active and placebo on the primary endpoint. We will use a cell-signaling Elastic Net (csEN) approach to detect immune features (functional cellular attributes as well as cell abundance) that separate the active and placebo groups, and we hypothesize that active treatment will be associated with immunomodulatory changes that have previously been associated with improved clinical recovery. While a classical power calculation has not been performed, previous interventional studies from the Stanford group have demonstrated that a sample of 40 subjects is a pragmatic sample that enables the detection of clinically-relevant immunomodulatory changes, such as changes in signaling downstream of immune receptors, including interleukin-1 and Toll-like receptor 4.

For secondary endpoints, the statistical approach toward efficacy endpoints will be primarily descriptive; within-subject changes from baseline for each dosing group and among-group differences will be evaluated. The most important clinical outcomes will be the SRS (time to 50% recovery of the baseline score), WOMAC Pain (time to mild pain as indicated by a score <12/40), and WOMAC Physical Function (time to mild functional impairment as indicated by a score <18/60).

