10.4 DESCRIPTION OF STATISTICAL METHODS

10.4.1 GENERAL APPROACH

Using the Evaluable and/or Per Protocol Datasets, all endpoints will be summarized serially over time using descriptive statistics to assess the within-subject changes and between-group differences. Overall baseline and demographic data will be summarized using descriptive statistics; between-groups testing will be used to evaluate the effectiveness of the randomization in producing homogeneous pre-treatment groups.

For analysis of the primary and secondary endpoints, the following will be considered:

- For endpoints that are continuous in nature:
 - Number of observations, mean, median, minimum, and maximum, and standard deviation (SD) values will be presented as descriptive summary
 - For inferential statistics:
 - If the Normality assumption is met, Paired t-test, or Analysis of Covariance (ANCOVA) using the baseline value as a covariate will be used
 - If the Normality assumption is not met, a rank –ANCOVA analysis i.e., an ANCOVA analysis on rank-transformed data or other non-parametric methods will be used
- For endpoints that are categorical in nature:
 - Frequency counts and percentages will be presented as descriptive summary
 - Chi-square test or Logit model will be used for inferential statistics

Subject disposition (e.g., the number of subjects randomized, completed, and discontinued) will be summarized, and medical history data will be listed. Prior and concomitant medications taken from screening and during the study will be categorized by World Health Organization classification for therapeutic class and drug name, listed and summarized by number and percentage of subjects.

Final analyses are not limited to the summaries described herein. As noted above, analytical details and assumptions will be fully presented in the SAP.

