10.6.3 BREAKING THE STUDY BLIND/SUBJECT CODE

The study blind can be broken for safety reasons if the information is required for the management of SAEs or severe AEs. Any noted intentional or unintentional breaking of the blind should be reported to the Sponsor's Program Physician. If unintentional unblinding occurs during the study, root cause analysis will be evaluated, and corrective actions implemented.

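### The supplied documents specify no all-randomised analysis of the clinical recovery endpoints; the protocol centres them on subjects who received all four doses

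*Protocol*

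**What the plan says.** Protocol 10.3 lists four datasets. Intention-to-Treat is everyone randomised, but the only use assigned to it is the baseline table. Safety analyses use everyone dosed. For the rest, "Analyses of the secondary endpoints will focus on the Evaluable and/or Per Protocol Datasets". Section 10.4.1 repeats the choice: "Using the Evaluable and/or Per Protocol Datasets, all endpoints will be summarized serially over time using descriptive statistics".

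Evaluable has two definitions. In 10.3 it is "all subjects who receive all 4 doses". In 10.1, and in the same words in 5.4.2, "Evaluable subjects are those who received all 4 doses and had all blood draws for assessment of the primary endpoint"; section 8.2 of the supplementary SAP also requires the blood samples. Per Protocol is, in 10.3, simply a subset of the Intention-to-Treat set with exclusion reasons left to the SAP. Supplementary SAP 8.2 makes it a subset of evaluable subjects.

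Section 6.1.8 adds: "The duration of therapy for a subject to be considered evaluable in the intent-to-treat population is 4 doses".

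The endpoints affected include those that section 10.2 ranks highest clinically, namely SRS and the WOMAC pain and physical function times to threshold.

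**The concern.** Randomisation precedes the first infusion. Infusions 2 to 4 come after exposure to study agent, and infusions 3 and 4 come after surgery. Whether a subject receives all four is therefore a post-randomisation event. Section 5.4 allows withdrawal for adverse events, section 2.3.1 names hypotension as a known risk, and section 8.4.3 lists edema and reduced kidney function as events of special interest. Infusion 3 is tied to a window after first incision, so a long or complicated operation could also interfere with it. Any of these can plausibly affect fatigue, pain, function, opioid use or length of stay.

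A comparison restricted to subjects with all four doses does not compare the arms as randomised. At stake is the reading of the recovery results. A difference between arms, or the lack of one, could partly reflect who was left out.

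**Working it through.** **1. Which set serves which purpose**

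| Purpose | Set named | Place |
|---|---|---|
| Baseline tables | All randomised | Protocol 10.3 |
| Safety | At least one dose | Protocol 10.3 |
| Secondary endpoints | Evaluable and/or Per Protocol | Protocol 10.3 |
| All endpoints, general approach | Evaluable and/or Per Protocol | Protocol 10.4.1 |
| CyTOF, ActiGraph, proteomics | Evaluable and Per Protocol; no all-randomised set | Supplementary SAP 8.2 |
| SRS, WOMAC, SF-36, BDI-II, opioids, discharge | Deferred to the clinical SAP of 08OCT2020, not supplied | Supplementary SAP 5 and 6.2 |

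No row gives a recovery endpoint an all-randomised analysis. Section 7.3.7 asks sites to obtain the Visit 15 assessments from early terminators, but a subject with fewer than four doses falls outside the Evaluable set, so no planned recovery analysis is assigned those data.

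**2. The plan's own figure**

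There is no power, effect size, SD or dropout rate to reproduce. The only figure is about 45 enrolled for 40 evaluable (Protocol 10.5):

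- 45 − 40 = 5, and 5/45 = 11.1%.
- 40/(1 − 0.10) = 44.4, rounded up to 45, so a 10% allowance fits equally well.

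This is not a dose-stopping rate. Under 10.1 and 5.4.2 the 40 must also have every blood draw, so the allowance covers missed samples too. Supplementary SAP 7.3 reports that enrolment ended with 37 evaluable subjects but not how many were randomised. If all 45 were randomised (an assumption), the loss is 8/45 = 17.8%.

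**3. How large the bias could be (illustration; every input is assumed)**

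Model: no true effect; 23 active and 22 placebo; recovery scored in SD units, higher is better. The k least tolerant active subjects are excluded and none from placebo. Tolerance and recovery have correlation r. There were 40,000 simulated trials per cell, with a two-sample t-test at two-sided 0.05. Cells show bias in favour of GRF6021 in SD, with the rejection rate in brackets.

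| r | k = 2 | k = 3 | k = 5 |
|---|---|---|---|
| 0 | 0.00 (5.0%) | 0.00 (5.0%) | 0.00 (5.0%) |
| 0.3 | 0.05 (5.1%) | 0.07 (5.7%) | 0.11 (6.3%) |
| 0.5 | 0.08 (6.1%) | 0.12 (6.9%) | 0.18 (8.9%) |
| 1.0 | 0.16 (9.7%) | 0.23 (13.7%) | 0.36 (24.3%) |

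Check: in this model the bias equals r times the bias at r = 1. At r = 0.5 that gives 0.5 × 0.162 = 0.081 for k = 2 and 0.5 × 0.360 = 0.180 for k = 5, against simulated values of 0.078 and 0.179.

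Scale: the standard error of the difference is √(1/21 + 1/22) = 0.305 SD for k = 2 and √(1/18 + 1/22) = 0.318 SD for k = 5. At r = 0.5 the bias is thus 0.08/0.305 = 0.26 to 0.18/0.318 = 0.57 of a standard error.

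The model is one-sided by construction. The same exclusions from placebo would give the same bias in the other direction, and exclusions alike in number and kind in both arms would cancel.

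**The case against.** The strongest reply is that the plan is less restrictive than it looks. Section 10.3 states a focus, not an exclusive rule. Section 10.4.1 says the final analyses may go beyond those listed. The document that governs these endpoints, the clinical SAP, has not been seen. A reader might infer that recovery will be analysed only in four-dose subjects, but the documents support no more than that no all-randomised analysis is specified in what was supplied.

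Three other stronger readings are tempting and also fail.

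- **Replacement and unblinding.** Section 5.4.2 says "Subjects who discontinue or are unblinded may be replaced", and 10.6.3 says "The study blind can be broken for safety reasons if the information is required for the management of SAEs or severe AEs". A reader might infer that poorly tolerating subjects are swapped for tolerant ones, with the arm known. Nothing says that a replaced subject's data are discarded. An unblinded subject with all four doses still meets the 10.3 definition of Evaluable. If the replacement is itself randomised, adding one does not shift the expected arm difference among completers. Who decides on replacement is not stated.
- **Section 6.1.8.** It can be read as redefining Intention-to-Treat as four doses. It can equally mean the evaluable subset of that population, which agrees with 10.3. It is loose wording, not a clear contradiction.
- **A large bias against placebo.** The 11.1% allowance might be taken as subjects who could not tolerate GRF6021. It includes missed blood draws, and no document supports a split by arm or a poor outcome in those who stop. Section 2.3.1 cites an infusion-reaction frequency of 0.002%, and section 4.1 allows the infusion to be adjusted for tolerability, which keeps subjects in the set.

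It is also fair to say that uneven stopping would be visible. Section 10.4.4 compares reasons for discontinuation across groups, the supplementary SAP plans a CONSORT diagram, and safety covers everyone dosed. The trial is an unpowered pilot with mainly descriptive secondary endpoints.

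These points limit the size and certainty of the problem but do not remove it. A disposition table shows that subjects were lost; it does not show the recovery comparison with them included. Selection distorts a descriptive contrast as much as a tested one, and 10.4.1 does provide for inferential tests.

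**Conclusion.** The point holds as a gap in specification. As written, the recovery comparison centres on a set defined by events after randomisation, and nothing supplied plans the comparison of the arms as randomised. That conclusion rests on the text and is subject to the unseen clinical SAP; if that SAP already has such an analysis, what remains is to align the protocol with it.

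The size is unknown. Bias arises only if stopping differs by arm and is linked to recovery. In the assumed range it runs from zero to about 0.08 to 0.18 SD (2 to 5 active-arm exclusions, correlation 0.5). The r = 1 row is a bound, not an expectation. The documents do not establish that GRF6021 will look better than it is.

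The change should be made because it is cheap and because section 10.2 gives these endpoints weight: "The most important clinical outcomes will be the SRS (time to 50% recovery of the baseline score" heads its list. It does not call the mechanistic primary analysis into question.

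**What to change.** - In Protocol 10.3 and 10.4.1 and in the clinical SAP, make all randomised subjects, in their assigned arm and regardless of doses taken or blood draws, the main set for SRS, WOMAC, SF-36, BDI-II, opioid use and time to discharge. Keep Evaluable and Per Protocol as supportive.
- Report by arm any randomised subjects who did not have surgery. Do not make surgery a condition of the set, because it comes after infusions 1 and 2.
- State that discontinued, unblinded or replaced subjects stay in the set and that their follow-up data are used, including the Visit 15 assessments already requested under 7.3.7. Where that is the only later assessment, time to threshold is known only to fall before or after it, so say how it enters the analysis.
- Reconcile 6.1.8 with 10.3, and choose one definition of Evaluable across 10.3, 5.4.2, 10.1 and supplementary SAP 8.2.

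Since enrolment has ended, this affects analysis and reporting, not who is replaced. If treatment codes are already open, label the analysis as added.

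The cost is wording and one more set of tables, with no extra subjects. The downside is slight dilution of the estimate by partly dosed subjects, which the supportive sets make visible. If few subjects stopped, the two analyses should largely agree.

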10.4 DESCRIPTION OF STATISTICAL METHODS

10.4.1 GENERAL APPROACH

Using the Evaluable and/or Per Protocol Datasets, all endpoints will be summarized serially over time using descriptive statistics to assess the within-subject changes and between-group differences. Overall baseline and demographic data will be summarized using descriptive statistics; between-groups testing will be used to evaluate the effectiveness of the randomization in producing homogeneous pre-treatment groups.

For analysis of the primary and secondary endpoints, the following will be considered:

- For endpoints that are continuous in nature:
 - Number of observations, mean, median, minimum, and maximum, and standard deviation (SD) values will be presented as descriptive summary
 - For inferential statistics:
 - If the Normality assumption is met, Paired t-test, or Analysis of Covariance (ANCOVA) using the baseline value as a covariate will be used
 - If the Normality assumption is not met, a rank –ANCOVA analysis i.e., an ANCOVA analysis on rank-transformed data or other non-parametric methods will be used
- For endpoints that are categorical in nature:
 - Frequency counts and percentages will be presented as descriptive summary
 - Chi-square test or Logit model will be used for inferential statistics

Subject disposition (e.g., the number of subjects randomized, completed, and discontinued) will be summarized, and medical history data will be listed. Prior and concomitant medications taken from screening and during the study will be categorized by World Health Organization classification for therapeutic class and drug name, listed and summarized by number and percentage of subjects.

Final analyses are not limited to the summaries described herein. As noted above, analytical details and assumptions will be fully presented in the SAP.

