10.4.3 ANALYSIS OF THE SECONDARY ENDPOINTS

Using available data from analysis of the secondary endpoints, descriptive summaries will be developed. Of particular interest will be the within-subject changes from baseline and their distribution around a null value of zero and a comparison between groups to evaluate any trends in differences between subjects randomized to active and placebo agents.

For safety endpoints, actual values and changes from baseline in clinical laboratory measurements and vital signs will be assessed and summarized. Abnormal lab or vital sign values will be determined and flagged in the listings. Laboratory shift tables or graphics displaying the change (number of subjects) relative to the reference range from baseline to each study visit may also be presented for each test. The investigator should exercise his or her medical and scientific judgment in deciding and documenting whether an abnormal laboratory finding, or other abnormal assessment is clinically significant.

For safety endpoints that are continuous in nature (e.g. clinical laboratory parameters, systolic and diastolic blood pressure, heart rate, respiratory rate, body temperature) the mean, median, minimum, maximum, and standard deviation will be plotted over time.

For safety endpoints that are categorical in nature (e.g. targeted physical exam or ECG abnormalities), the frequency counts and percentages will be presented as a descriptive summary.

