10.5 SAMPLE SIZE

A total of approximately 45 subjects will be enrolled with the aim of having 40 evaluable subjects randomized in a 1:1 ratio to active treatment or placebo. The primary endpoint of this study (differences in immunological and/or proteomic signatures among patient groups), the principal computational approach (machine learning) used, and the exploratory nature of the study prevent a traditional power analysis. However, a sample size of 2 x 20 subjects was sufficient to detect relevant differences in previous studies examining interventions expected to have a similar effect size ([Aghaeepour 2017](#)).

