10.6 MEASURES TO MINIMIZE BIAS

10.6.1 ENROLLMENT/RANDOMIZATION

To minimize the potential bias at the time of randomization, the study will be randomized in a 1:1 ratio (active: placebo), stratified by sex and surgical joint (hip, knee) to assure a balanced distribution of evaluable male and female subjects in both treatment groups.

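### Protocol 10.4.1 offers a paired t-test as interchangeable with ANCOVA, but it tests within-arm change and cannot estimate GRF6021 versus placebo; the ANCOVA as stated omits the stratification factors

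*Protocol*

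**What the plan says.** Protocol 10.4.1 introduces its list of methods with "For analysis of the primary and secondary endpoints, the following will be considered". For continuous endpoints, under inferential statistics, it gives: "If the Normality assumption is met, Paired t-test, or Analysis of Covariance (ANCOVA) using the baseline value as a covariate will be used". If Normality fails, it turns to rank-ANCOVA or another non-parametric method. Nothing says when the paired test applies and when the ANCOVA does.

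The protocol has two aims. Section 10.4.1 calls for "descriptive statistics to assess the within-subject changes and between-group differences", and section 10.4.3 takes particular interest in "within-subject changes from baseline and their distribution around a null value of zero and a comparison between groups". Section 10.2 says that "the statistical approach toward efficacy endpoints will be primarily descriptive".

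Under section 10.6.1, randomisation is 1:1 and "stratified by sex and surgical joint (hip, knee"). No method in 10.4.1 names either factor; the only covariate given for the ANCOVA is the baseline value.

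The SAP supplied is a supplementary plan. Its section 8.1 assigns elastic-net methods to the CyTOF, ActiGraph and proteomics endpoints. Its section 5 places the remaining clinical and safety endpoints in a separate SAP of 08OCT2020, which is not among the documents reviewed.

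**The concern.** The two tests joined by the word or answer different questions. In a two-arm parallel trial the natural pairing is baseline with follow-up in the same subject, so the paired t-test asks whether one arm changed. Every subject has a hip or knee replacement between those measurements, so change is expected in both arms whatever GRF6021 does. Only the ANCOVA estimates the treatment difference.

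As written, an analyst could run a paired test in each arm, find one significant and the other not, and report this as the inferential result for the endpoint while staying within the protocol. That comparison of two p-values is not a test of the difference between arms, and its error rate is not 5%.

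The second issue concerns the ANCOVA itself. Stratified randomisation balances sex and joint between arms. A model that leaves them out still counts their contribution as residual noise, so the test is conservative and loses power if these factors affect outcome.

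**Working it through.** The documents give no power, effect size or SD for a continuous endpoint, so there is no figure of the plan to reproduce.

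**Inputs from the documents**
- 37 evaluable subjects (SAP 7.3), 1:1 allocation (protocol 10.6.1).
- Alpha 0.05 (SAP 8.1).
- Strata: sex and surgical joint (protocol 10.6.1).

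**Assumptions, not in the documents**
- Split of 19 active and 18 placebo; two-sided tests.
- A common change d in both arms, in SDs of the change score, with no drug effect.
- For step 3: outcome SD 1 within strata, baseline correlation 0.5, strata nearly balanced between arms, and a difference of 0.5 SD between the two levels of each stratum factor.

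**Step 1. Paired test in one arm, no drug effect.** The chance of significance is P(n, d) = Pr(|T| > t), where T is non-central t with n − 1 degrees of freedom and non-centrality d√n, and t is the two-sided 5% critical value. At d = 0.5:
- n = 19: non-centrality 0.5 × √19 = 2.18, giving 0.541.
- n = 18: non-centrality 0.5 × √18 = 2.12, giving 0.516.

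**Step 2. One arm significant, the other not.** The arms are independent, so:
- active only = P(19) × [1 − P(18)];
- exactly one = P(19) × [1 − P(18)] + P(18) × [1 − P(19)].

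At d = 0.5, active only = 0.541 × 0.484 = 0.26, and exactly one = 0.26 + 0.516 × 0.459 = 0.50.

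| Common change (SD) | P(19) | P(18) | Active only | Exactly one arm |
|---|---|---|---|---|
| 0 | 0.050 | 0.050 | 5% | 9.5% |
| 0.25 | 0.178 | 0.170 | 15% | 29% |
| 0.5 | 0.541 | 0.516 | 26% | 50% |
| 0.8 | 0.909 | 0.892 | 10% | 18% |
| 1.0 | 0.985 | 0.979 | 2% | 4% |

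The peak is near 0.5 SD, where each arm has roughly even odds of significance. For large changes both arms are almost always significant. At the planned 20 per arm, exactly one arm is significant in 30%, 49%, 14% and 2% of trials at 0.25, 0.5, 0.8 and 1.0 SD, so the smaller final sample matters little here.

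The active arm taken alone is significant in 54% of trials at 0.5 SD and 98% at 1.0 SD with no drug effect: the paired test responds to surgery and recovery.

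**Step 3. ANCOVA with and without strata.** Residual variance after baseline is 1 − 0.5² = 0.75. A balanced two-level factor with a 0.5 SD difference adds 0.25² = 0.0625, so two factors add 0.125. The baseline-only model therefore estimates a residual variance near 0.875. With balanced strata, the treatment estimate varies only as 0.75 implies. The standard error is overstated by about √(0.875/0.75) = 1.08, and the effective normal critical value is 1.96 × 1.08 = 2.12, a true two-sided level of about 3.4%. Simulation at 19/18 agrees:

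| Each stratum effect | Model covariates | Null rejection | Power at 0.8 SD |
|---|---|---|---|
| 0.5 SD | baseline | about 4% | about 72% |
| 0.5 SD | baseline, sex, joint | about 5% | about 77% |
| 0 | baseline | about 5% | about 77% |
| 0 | baseline, sex, joint | about 5% | about 77% |

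Residual degrees of freedom fall from 37 − 3 = 34 to 37 − 5 = 32.

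**The case against.** The strongest reply is that the protocol names both aims wherever it discusses these analyses, so the natural reading is a paired test for change within an arm and ANCOVA for the comparison between arms. The listed methods are only to be considered, the secondary analysis is primarily descriptive, the study is an unpowered pilot, and details are left to a SAP that was not supplied. The reach is also narrow. The primary, ActiGraph and proteomics endpoints use elastic nets, and the three most important clinical outcomes in section 10.2 are times to an event. What remains is chiefly SF-36, BDI-II, end-of-study WOMAC, laboratory values and vital signs.

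Most of this stands as a limit on the point. It does not supply the missing sentence: 10.4.1 provides for inference and joins the two tests without assigning either to an aim.

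A reader might infer more than the documents support:
- **That the paired test ignores baseline.** It does not; baseline is half of every pair. What it lacks is a comparison arm and covariate adjustment.
- **That omitting the strata is a fault of the paired test alone.** The stated ANCOVA omits them too, so deleting the paired test would not cure it.
- **That the false-positive rate is 50%.** That is the near-peak chance of exactly one arm being significant, in either direction. Active-only significance peaks near 26%, and both figures fall below 5% at 1.0 SD.
- **That the trial will read one-arm significance as a drug effect.** No section says so; the text merely fails to rule it out.

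**Conclusion.** The point holds in a limited form. Protocol 10.4.1 lists as alternatives two tests that answer different questions, and only one of them estimates the effect of GRF6021. If p-values from the two arms were compared, the misleading pattern of active significant and placebo not would arise in about 2% to 26% of null trials for a common change between 0.25 and 1.0 SD. That range depends on the assumed change and the assumed 19/18 split.

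The missing strata are a separate and smaller loss: about five percentage points of power at 0.8 SD if each stratum effect is 0.5 SD and the baseline correlation 0.5, and essentially none if the stratum effects are near zero. The error is in the conservative direction.

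The point concerns continuous endpoints with a baseline value. It does not touch the primary analysis in the SAP supplied, and the clinical SAP of 08OCT2020 may already resolve it.

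**What to change.** For continuous endpoints with a baseline value (for example SF-36, BDI-II and end-of-study WOMAC), state that the between-arm test is ANCOVA with baseline value, sex and surgical joint as covariates, and rank-ANCOVA with the same covariates when Normality fails. State that the paired analysis is supportive within-arm description only, reported as mean change with a 95% confidence interval, and is not evidence of a drug effect.

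Leave time-to-event endpoints, categorical endpoints and perioperative measures without a baseline (such as surgery duration or blood loss) to their own methods; a baseline ANCOVA does not suit them.

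Check the clinical SAP of 08OCT2020 first. If it already says this, only the protocol wording needs aligning.

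The cost is a few lines of text and two residual degrees of freedom. Sex and joint are already recorded for randomisation, so no new data are needed.
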